Phone sessions (11)	15-20 minutes in length; conducted individually with patient and SO; follows schedule of decreasing frequency (weekly in first two months, biweekly in next two months, monthly thereafter); calls start with brief assessment of risk factors, with patient safety taking priority; problems around treatment engagement and adherence addressed next, with main strategy to engage in active service linkage, if required (e.g., facilitating intake appointments at the CMHCs where counselors are already employed) and also to facilitate communication between patient and SO; problems addressed in context of Re-Entry Plan values and goals; if a problem develops that cannot be addressed in this manner, therapist may obtain permission to contact patient’s community treatment provider(s) (if already service connected) and/or temporarily increase frequency of contacts during times of crisis; SO contact proceeds in a similar manner

transition back to the community. A copy of the participant's "Re-entry Plan" will be mailed to his/her home after his/her release from prison or after completion if recruited post-release. The family intervention component will also be facilitated by the post-release telephone contacts between the provider and the patient and the SO. Telephone contacts are used to: a) identify, monitor, and address problems in relevant areas (e.g., sobriety, treatment utilization), b) encourage additional support and open communication, and c) facilitate problem-solving and concrete service linkage to reduce barriers to treatment engagement and progress toward values-consistent goals.

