In the Pilot Randomized Trial Phase, if a participant is determined to be eligible following the baseline assessment, s/he will be randomized to either E-TAU plus CARE or to E-TAU alone.

**Randomization** will be determined in a 1:1 ratio, with 2 stratification variables, the maximum number advisable in a sample of this size: sex (male vs. female) and polarity of most recent mood episode (depression vs. (hypo)mania) using a randomization table.

Participants randomized to receive CARE will receive 4 counseling sessions. The first 3 sessions will be individual sessions that take place in prison in the time between the baseline assessment and the anticipated date of release from prison; or they will take place after release for those enrolled post-release. A fourth session will either be an individual counseling session or a family/SO session (as applicable). This session will take place either in prison prior to release or as soon as possible after release either by telephone, by zoom, or in person (e.g., at our offices or in any residential facility where the participant is located, with facility approval). Ideally, the first two sessions will be delivered within 1 week, the third session will be delivered within the following week, and the fourth session will be delivered within the week after that as either an individual session or a family/SO session. However, we acknowledge that time to release will be variable, and the session schedule may be compressed or spread out depending upon length of time available to complete the sessions between the baseline assessment and the prison release date. Following prison release (in prison enrollment) or completion of the initial sessions (post-release enrollment), the counselor will initiate the phone follow-up calls, delivered across the first 6 months post-release (in prison enrollment) or 6 months post-baseline (post-release enrollment). The schedule for phone follow-up will be: weekly for the first month, biweekly for the next 2 months, and then monthly for the final 3 months. Calls will be made separately to the prisoner participant and to the identified SO (if applicable).

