Assessments will occur on the following schedule: For participants recruited in person at [REDACTED] prior to release: a) baseline assessment; b) following the in-prison sessions, prior to prison release (~1-2 weeks prior to prison release); c) 1 month after prison release; and d) 6 months after prison release, immediately post-treatment. For participants recruited post-release: a) baseline assessment; b) 1 month after baseline; and c) 6 months after baseline, immediately post-treatment. The post-release enrollment baseline would include any additional questionnaires/items from the pre-release assessment that were not already included in the baseline assessment. To enhance feasibility and retention, we will aim to complete all post-release follow-up assessments by telephone or zoom, using procedures we have in place for other studies (see "Human Subjects Protections"). However, there may be some circumstances that might make it difficult for a participant to complete the follow-up assessment by telephone or zoom (e.g., limited phone minutes, participant rearrest and reincarceration, current enrollment in a residential treatment program). In such cases, we will complete the follow-up assessment in person in our offices at [REDACTED] or in the facilities where the participant may be located (e.g., jail or prison, residential treatment facility). Additionally, if a participant is released earlier than expected before finishing the in-prison assessment, we will complete the assessment by

telephone, by zoom, or in person at our offices or in the facility (e.g., residential treatment program) where the participant is located.

Appointments for participants randomized to the E-TAU condition will consist of the regularly scheduled research assessments. For participants recruited in person at [REDACTED] prior to release: baseline, pre-release, 1 month post-release, and 6 months post-release. For participants recruited post-release: baseline, 1 month after baseline; and 6 months after baseline. The post-release enrollment baseline would include any additional questionnaires/items from the pre-release assessment that were not already included in the baseline assessment.

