### **3.b.8. Assessment procedures.**

Participants enrolled prior to release will be assessed at: intake, just prior to prison release (4-10 weeks later, depending upon timing of baseline and scheduled release date), and then at 1 and 6 months post-release. Participants enrolled post-release will be assessed at: intake, and then at 1 and 6 months post-release. The post-release enrollment baseline will consist of any items in the pre-release that were not included in the baseline. In addition to demographics, we will assess psychiatric diagnosis (primary inclusion criterion), psychiatric symptom severity, substance use history, psychosocial functioning, proposed mechanisms of action for the intervention (i.e., values-action consistency, social support, mental health and substance use treatment utilization and adherence), and treatment satisfaction. Assessments are listed in Table 2. RAs will also call to verify/update locator information monthly after release.

All interview and self-report assessment measures were chosen because they have strong psychometric properties for measurement of the constructs of interest to the study, and have been used in other NIH-funded clinical trials and prospective studies. With signed releases of information (ROIs) obtained at the baseline assessment, we will supplement interview and self-report data with criminal justice and medical records chart review to assess for recidivism and community treatment utilization, respectively.

Table 2: Pre-Release Enrollment Schedule of Assessments	Type	Baseline	Pre-release, 1mo & 6mo post- release
Diagnosis: Structured Clinical Interview for DSM-5 	Interview	X	
Psychiatric Symptom Severity			
LIFE – PSRs for depression and mania 	Interview	X	X
Quick Inventory of Depressive Symptomatology 	Self-report	X	X
Altman Self-Rating Scale for Mania 	Self-report	X	X
LIFE – suicidal ideation and behavior 	Interview	X	X
Substance Use			
Alcohol Use Disorders Identification Test 	Self-report	X	1 & 6 mo only
Drug Use Disorders Identification Test 	Self-report	X	1 & 6 mo only
Psychosocial Functioning			
SF-12 from RAND Medical Outcomes Study 	Self-report	X	X

Job Security Index/Job Satisfaction Scale 	Self-report		1 & 6 mo only
Housing Security Scale 	Self-report		1 & 6 mo only

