### **3.c.6. Safety Monitoring Plan**

[REDACTED] will be responsible for overseeing the safety of all participants. [REDACTED] (who maintains her clinical license in RI) will be available to serve as clinical back-up for [REDACTED], when required. [REDACTED], study co-investigator, is a board-certified psychiatrist who will serve as the medical advisor. Participant safety will be monitored in two ways: (a) during the intake or ongoing assessments by the research staff, or (b) during intervention sessions. Research assessments will be conducted in the prison at study intake, at pre-release (4-10 weeks later), and in the community at 1 and 6 months post-release. We will monitor all participants for significant suicidal ideation (SI), homicidal ideation (HI), and clinical deterioration at each time point.

**During incarceration** the [REDACTED] standards for mandatory reporting of suicide risk specify that we are required to report anyone who has had suicidal ideation within the past 24 hours (as determined by a QIDS item 12 score > 1, LIFE PSR > 2, or reporting any current desire to hurt oneself to any member of the research staff). If the participant reports this level of SI within the past 2 weeks, but not in the 24 hours prior to the assessment, a voluntary referral will be offered. Participants meeting the prison's SI mandatory reporting criteria (or those who elect the voluntary referral) will be referred to a prison mental health clinician for evaluation, who will follow prison procedures. Standard prison procedures include: (1) checking in the prison's electronic medical record to see if the person has already been flagged as having SI; (2) having a licensed mental health clinician check in with the person and do a suicide risk evaluation; and/or (3) if needed, putting the person on psychiatric observation within the prison. If the prison mental health professional determines that someone's risk has gone down, that person will leave

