The study will rely upon the NIH's definitions for Common Adverse Events (AEs) and Serious Adverse Events (SAEs) for clinical research, and definitions will be operationalized in the approved study protocol document and manual of procedures (MOP). We will require that all study staff, study interventionists, and study participants report any adverse events to [REDACTED] immediately. These include, but are not limited to, psychiatric hospitalization and/or suicide attempt. Consistent with procedures utilized in our other psychosocial treatment studies for prisoners, jail detainees, and other high risk psychiatric samples, [REDACTED] will be available by telephone, by zoom, or in person during all participant assessments in the event that immediate consultation is needed for an emergent mental health or other problem. If an AE occurs, [REDACTED] will complete an Adverse Event form and report the event to the [REDACTED] IRB per their reporting guidelines and timeline. [REDACTED] will also review the adverse event form with the investigator team. They will gather any information needed to investigate the event and to determine subsequent action; this will also be reported to the IRB. We will inform NIH of any significant action taken as a result of any adverse event report. Anticipated and less serious adverse events will be submitted annually in reports to the IRB.

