### **3.c.7. Data Safety and Monitoring Board**

An external local DSMB will be assembled to evaluate the data and safety to participants enrolled in the study. We will recruit 3 [REDACTED]-affiliated board members who have experience in clinical trials and/or BD treatment research and/or research with criminal justice samples as well as the ethical issues involved with a randomized control study. The external DSMB will convene twice in Year 1, and then at the end of each year in Years 2-3 for a meeting. Initially, the Board will convene with the PI and study Co-Is to review the study protocol and review the guidelines for data and safety monitoring. At this meeting and at each subsequent meeting, the DSMB will evaluate recruitment, the progress of the trial, subject retention, data quality and confidentiality. In addition, they will review participants' clinical status, rates of adverse events and whether or not there have been any changes in risk to participants.

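### Adverse events reach the study through research assessments in both arms but through counselor contacts in CARE only, so an all-source by-arm AE rate would tend to over-count CARE at equal risk

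*Combined protocol and SAP*

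**What the plan says.** **Routes.** Section 3.c.6 (Safety Monitoring Plan): "Participant safety will be monitored in two ways: (a) during the intake or ongoing assessments by the research staff, or (b) during intervention sessions". The same section requires that "all study staff, study interventionists, and study participants report any adverse events" at once.

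**E-TAU.** Section 3.b.6 (Participant Timeline): "Appointments for participants randomized to the E-TAU condition will consist of the regularly scheduled research assessments". After release, or after baseline for those enrolled in the community, these fall at months 1 and 6.

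**CARE.** Section 3.b.6 adds four sessions and a series of calls, timed "weekly for the first month, biweekly for the next 2 months, and then monthly for the final 3 months". Table 1 in section 3.b.2 says that "calls start with brief assessment of risk factors, with patient safety taking priority". Separate calls go to the significant other where there is one.

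**Routes open to both arms.** Section 3.b.8 (Assessment procedures): "RAs will also call to verify/update locator information monthly after release". No safety question is specified for these calls. The LIFE, the Treatment History Interview and records review are scheduled without restriction by arm.

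**Use of the counts.** Section 3.c.7: "The external DSMB will convene twice in Year 1, and then at the end of each year in Years 2-3 for a meeting". The items reviewed include "rates of adverse events and whether or not there have been any changes in risk to participants". Section 3.b.9 contains no AE analysis, and no section gives the source of the counts, the denominator, the time window or a split by arm.

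**The concern.** The arms differ in how often someone who must report AEs is in touch with the participant. The contact is part of CARE and should stay. The QIDS and ASRM deterioration thresholds are not affected at the research assessments, because those scales are taken there on the same schedule in both arms. The problem is confined to AE counts. If an E-TAU participant is hospitalized in month 2, the next scheduled assessment is at month 6. For a CARE participant the next scheduled call is at most a month away.

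With 20 participants per arm, a few more reported events in CARE could be read as harm when only detection differs, or could mask a real reduction. The reader could be the DSMB, or the designers of the larger trial described in section 3.c.9. If the rates are pooled over arms instead, this distortion does not arise, but the DSMB cannot see any effect of CARE on risk.

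**Working it through.** **1. Call count.** The section 3.b.6 schedule gives 4 weekly + 4 biweekly + 3 monthly = 11 calls, which matches the stated 11. After month 1 there are 4 + 3 = 7. Table 1, labelled tentative, has a different frequency: 8 + 4 + 2 = 14, which does not match 11. I use the section 3.b.6 schedule. E-TAU has no assessment strictly between months 1 and 6, but up to about 5 locator calls from month 2 to month 6.

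**2. Interim count, extreme case.** The documents give no AE rates or reporting behavior, so what follows is assumed:
- a constant and equal event rate in both arms;
- every participant mid-follow-up, with time since release uniform on 0 to 6 months (mean 3.0);
- events known only from scheduled contacts, that is, when they precede the last contact.

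Contacts are at months 1 and 6 in E-TAU. CARE adds calls at 0.25, 0.5, 0.75, 1, 1.5, 2, 2.5, 3, 4, 5 and 6.

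- E-TAU mean known time: (1 × 5)/6 = 0.83 months; 0.83/3.0 = 27.8%.
- CARE: [0.25 × (0.25 + 0.5 + 0.75) + 0.5 × (1 + 1.5 + 2 + 2.5) + 1 × (3 + 4 + 5)]/6 = 15.875/6 = 2.65 months; 88.2%.
- Apparent ratio: 15.875/5 = 3.2.
- With each call made with probability 6/11 (the call part of the completion criterion in section 3.b.9), CARE known time is 2.25 months (75.1%) and the ratio is 2.7.

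**3. Relaxing the assumptions (all calls made).** Let a share s of events reach the study at once by other routes. The ratio is [s + (1 − s) × 0.882]/[s + (1 − s) × 0.278].

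| Situation | Apparent CARE/E-TAU ratio |
|---|---|
| s = 0.25, 0.50, 0.75, all mid-follow-up | 1.99, 1.47, 1.18 |
| Half of each arm finished, full recall, s = 0 to 0.75 | 1.27 to 1.05 |
| Three quarters finished, full recall, s = 0 to 0.75 | 1.10 to 1.02 |
| Locator calls catch every event in both arms | 1.06 (1.04 at 6/11 calls) |

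Half finished, s = 0: (0.5 × 6 + 0.5 × 2.65)/(0.5 × 6 + 0.5 × 0.83) = 4.32/3.42 = 1.27. Locator row: E-TAU known time is (0 + 1 + 2 + 3 + 4 + 5)/6 = 2.5 months (83.3%), and 88.2/83.3 = 1.06.

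**4. Final count.** Let month-6 attendance be a (0.7, 0.8, 0.9), recall r (0.7, 0.85, 1) and counselor capture c (0.3, 0.5, 0.8). E-TAU captures a·r and CARE captures 1 − (1 − a·r)(1 − c). Over the 27 combinations the ratio runs from 0.93/0.90 = 1.03 to 0.898/0.49 = 1.83, with median 1.24. This gives records review no separate role. If records independently capture a share q of 0.5 to 0.9 in both arms, each miss probability is multiplied by (1 − q). The range becomes 1.00 to 1.27, with medians of 1.02 to 1.09.

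**5. What 20 per arm would show.** A Poisson simulation (40,000 runs) assumed 0.5 events per person per 6 months and equal true risk. An apparent excess was defined as CARE showing at least double the E-TAU figure and 3 or more extra events. It appeared in 56% of trials in the extreme case of step 2, against 7% under the common-source rule proposed below. With half of each arm finished it was 25% against 15%. The mean rate ratio under the common-source rule was 0.99 to 1.00.

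**The case against.** The strongest reply has five parts.

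**No stated comparison.** Section 3.c.7 names no by-arm test, threshold or stopping rule, and a change in risk may mean change over time. A reader might infer that the DSMB will see a false signal of harm and act on it. The documents do not support that. This part stands and limits the claim to a risk.

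**The largest ratio is implausible.** A reader might take the figure of about 3 as the expected bias. It needs everyone mid-follow-up and no other reporting route. The 12-person open trial comes first, and the DSMB meets only yearly after Year 1, so early meetings probably see single-arm data and the last one mostly finished participants. This stands: the half-finished and three-quarters-finished rows are the more likely range.

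**Other routes exist.** A reader might infer that E-TAU events go unseen for five months. Research assistants telephone monthly without restriction by arm, all staff and participants must report AEs, and records review does not depend on attending month 6. This stands as a limit on size. These routes narrow the gap, but the locator calls have no stated AE question and none of the routes removes the CARE-only one.

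**Detail may sit elsewhere.** Section 3.c.6 defers AE and SAE definitions to the protocol and manual of procedures, and the DSMB is to review monitoring guidelines at its first meeting. A rate rule could be set there. But what is expressly deferred is what counts as an event, not how rates are formed.

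**The remedy is partial.** The all-source listing would still show the raw imbalance, and with half finished much of any apparent excess is small-sample noise (15% remains). CARE aims to raise treatment use, which can itself increase capture through records. Both points stand as limits of the fix.

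**Conclusion.** The asymmetry is in the text: a monitoring route that only CARE has, run by people obliged to report AEs, feeding rates that the plan does not define. Any by-arm rate built from all sources will tend to be too high in CARE relative to E-TAU at equal true risk. The direction is the same throughout the scenarios examined; the size is not known. It is near 1.0 if the shared routes recover most events, about 1.05 to 1.27 with half of each arm finished, and about 3 only in the extreme case. All these figures rest on assumed event rates, reporting shares, attendance, recall and timing.

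The plan should be amended because the improvement is inexpensive, not because a wrong safety conclusion has been shown. Confidence is medium.

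**What to change.** - **Ask.** At every research assessment in both arms, put one fixed AE question covering the time since the last assessment. The assessors of follow-up are blind to condition (section 3.c.5); they should ask it without being told of counselor reports.
- **Record.** Add two fields to the AE form: the first source of the event, and whether a common source (assessment question, LIFE, Treatment History Interview or records review) also elicited it.
- **Report.** Define in sections 3.b.9 and 3.c.7 a by-arm common-source AE rate. The numerator is common-source events; the denominator is person-time to each participant's last completed assessment, not to the data cut. Show it beside an all-source listing by arm that marks counselor-only events.
- **Optional.** Put the same question in the existing monthly locator calls in both arms, which narrows the gap directly.

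Cost: one scripted question, two form fields and one table layout. No new contact is needed, nothing in CARE or E-TAU is removed, and every event is handled clinically as now.

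Downside: the common-source rate is less current, omits counselor-only events, and may not be fully neutral if CARE increases treatment use and hence capture through records. The all-source listing is kept for that reason.

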### **3.c.7. Data Safety and Monitoring Board**

An external local DSMB will be assembled to evaluate the data and safety to participants enrolled in the study. We will recruit 3 [REDACTED]-affiliated board members who have experience in clinical trials and/or BD treatment research and/or research with criminal justice samples as well as the ethical issues involved with a randomized control study. The external DSMB will convene twice in Year 1, and then at the end of each year in Years 2-3 for a meeting. Initially, the Board will convene with the PI and study Co-Is to review the study protocol and review the guidelines for data and safety monitoring. At this meeting and at each subsequent meeting, the DSMB will evaluate recruitment, the progress of the trial, subject retention, data quality and confidentiality. In addition, they will review participants' clinical status, rates of adverse events and whether or not there have been any changes in risk to participants.

### **3.c.8. Benefits of the Proposed Research to the Subjects and Others**

The potential risks associated with participation in this study appear to be mild to moderate. Although there is a risk for distress, the procedures proposed for monitoring distress should ensure that participants who require a higher level of care receive it. The study provides additional screening, assessment, and referral to emergency services, as needed, for all study participants, and in no way restricts or limits the treatment individuals would have received had they not participated in the study. Moreover, participants are helping other incarcerated individuals with BD by providing information that will improve treatments for this population. Thus, the potential benefits outweigh the potential risks of the study.

